Week 4	25	25	30	40
Week 6	20	20	20	30
Week 8	15	15	15	20
Week 10	10	10	10	10
Week 12	7.5	7.5	7.5	7.5
Weeks 24-80	5	5	5	5

Oral prednisone is started at 0.5 mg/kg/day (maximum 60 mg/day). Starting doses should be rounded to the nearest 10 mg dose or the nearest dose that is feasible based on the locally available oral prednisone dose strengths. An approximately equivalent dose of an oral corticosteroid with a similar duration of action may be substituted.

Corticosteroid Dose Increases

Treatment with higher doses of prednisone is permitted if judged clinically necessary by the investigator for renal and extrarenal flares (see Appendix 5). Use of intravenous corticosteroids during the study is strongly discouraged unless gastrointestinal involvement temporarily precludes the use of oral corticosteroids.

Patients may receive higher doses of corticosteroids for emergent illness or surgery if clinically indicated; the corticosteroid use should be limited to the minimum duration and dose necessary before resuming the prednisone taper.

Use of pulse steroids or sustained, high-dose corticosteroids from Week 64 onward is considered corticosteroid rescue, will result in nonresponse for subsequent efficacy assessments, and should be avoided (see Section 4.4.4.1).

Corticosteroid Treatment after Week 80

After Week 80, the prednisone dose may be adjusted at the discretion of the investigator. Oral prednisone should not be administered on days when pre-infusion methylprednisolone is given.

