- Intercurrent events: Rescue therapy, treatment failure, study treatment discontinuation, or death prior to endpoint assessment. Rescue therapy, treatment failure and study treatment discontinuation will be handled using treatment policy strategy.
 - Death will be handled using composite strategy. Data after death will be imputed by a pre-specified single fixed value specified in the next sections for each of the continuous endpoints.
- Summary measure: Difference in adjusted means at a specified visit of interest

The intercurrent events are described in Section 4.2.1.1.

4.3.1 Key Secondary Endpoints

4.3.1.1 Proportion of Patients who Achieve a Proteinuric Response at Week 76

The proportion of patients who achieve a proteinuric response at Week 76 will be analyzed using a CMH test with region and race as stratification factors. Proteinuric response is defined as achievement of all of the following:

- UPCR < 0.8
- No occurrence of the following intercurrent events:
 - Rescue therapy, treatment failure, death, or early study withdrawal

Missing data: Data obtained from the central laboratory only will be used. UPCR will be imputed by multiple imputations using the model specified in Section 4.2.2. The same imputed datasets produced during the analysis of CRR will be used for the analysis of proteinuric response. The analysis will follow the same methods described in Section 4.2.2.

4.3.1.2 Proportion of Patients who Achieve CRR with Successful Prednisone Taper at Week 76

The proportion of patients who achieve CRR with successful prednisone taper at Week 76 is defined as achievement of CRR (defined as Section 4.2.1) at Week 76 with the following:

 No receipt of prednisone >7.5 mg/day (or equivalent) from Week 64 through Week 76

The endpoint will be analyzed using a CMH test with region and race as stratification factors.

Only oral corticosteroid will be considered for evaluating the no receipt of prednisone >7.5 mg/day (or equivalent) criteria and converted to prednisone equivalent dose when applicable.

Data Handling for Oral Corticosteroids

The study team will monitor oral corticosteroids on an ongoing basis for data quality and to ensure all dose adjustments are being correctly captured. All efforts will be made to resolve missing or ambiguous data prior to database lock. In the case that data queries cannot be resolved, data will be handled in a conservative manner as described in the sections below.

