The intervals for each dose of oral corticosteroid captured during the taper are expected to be continuous and non-overlapping. Patients who are adequately controlled by their blinded treatment may discontinue oral corticosteroids altogether, but may re-start treatment as required to treat any increases in disease activity. With this in mind, the use of available data will be maximized and incorporated into the imputation of missing or partial dates as follows:

Missing Term	Imputation Method
Start Date	
Missing Day	Latest of the following:
	Previous End Date+1
	First day of the month
Missing Month/Year	Previous End Date+1
End Date	
Missing Day	Earliest of the following:
	Next Start Date-1
	Last day of the month
Missing Month/Year	Next Start Date-1

Within two consecutive dosing intervals, if the end date of the first dose interval is missing or partially missing and the start date of the second dose interval is missing or partially missing, a midpoint approach using the start date of the first interval and the end date of the second interval will be used to assign a cut-off end date, providing these dates are available.

A missing or 'ongoing' final end date will be imputed with clinical cutoff date (CCOD) or the date of withdrawal from the study in case a patient withdraw early from the study. A missing initial start date will be imputed with Day 1 providing the end date is after Day 1, otherwise no imputation will be made.

If there is a start and/or end date, but the total daily dose is missing then the dose will be imputed using the dose from the previous dose.

In the event of overlapping dose intervals, the patient will be assumed to be taking the higher dose for the maximum amount of time possible such that the total daily dose will never be double counted.

Missing UPCR and eGFR Data

Missing UPCR and eGFR data will be imputed by multiple imputations using the model specified in Section 4.2.2. The same imputed datasets produced during the analysis of CRR (described in Section 4.2.2) will be used for this analysis. The CRR with successful prednisone taper at Week 76 will be derived for each datasets. The analysis will follow the same methods described in Section 4.2.2.

4.3.1.3 Proportion of Patients who Achieve an ORR, Defined as Achievement of Either CRR or PRR, Evaluated at Week 50

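### The SAP scores overlapping oral steroid records at the higher dose, so confirmed concurrent use totalling more than 7.5 mg/day can pass as a successful taper when each record alone is 7.5 mg/day or less

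*SAP*

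**What the plan says.** SAP 4.3.1.2 requires CRR at Week 76 together with "No receipt of prednisone >7.5 mg/day (or equivalent) from Week 64 through" Week 76. On route it says "Only oral corticosteroid will be considered for evaluating the no receipt of prednisone >7.5 mg/day (or equivalent) criteria", with conversion to prednisone equivalent where applicable.

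The data-handling part of that section says that oral steroid data are monitored during the study and that missing or ambiguous entries are pursued before database lock. It then says: "In the case that data queries cannot be resolved, data will be handled in a conservative manner". Dose intervals are "expected to be continuous and non-overlapping". The quantity attached to an interval is called a total daily dose: "If there is a start and/or end date, but the total daily dose is missing then the dose will be imputed", using the previous dose. When intervals do overlap, the patient is "assumed to be taking the higher dose for the maximum amount of time possible such that the total daily dose will never be double counted". No exception is made for a different agent or for confirmed co-administration, and no other rule in the SAP says how such days are scored.

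Protocol 4.3.2.1 schedules prednisone at 5 mg/day from Week 24 to Week 80, lets an equivalent oral steroid be substituted where prednisone is not readily available, and adds: "Patients may receive higher doses of corticosteroids for emergent illness or surgery if clinically indicated". Protocol 4.4 has drugs taken in addition to protocol treatment recorded on the Concomitant Medications eCRF.

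Under SAP 2.1.1 this endpoint is tested first among the key secondaries, at two-sided 0.05. If it is not significant, testing stops.

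**The concern.** The criterion is about the dose a patient received. When two oral steroids are taken on the same day, the dose received is their sum, but the SAP counts only the larger. For those days the rule can only lower the counted dose and so favour success. That is the opposite of the stated intent that "data will be handled in a conservative manner as described in the sections below".

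Separate overlapping records are foreseeable. A base dose and an added course, or two agents, could be entered as two lines, one of them on the concomitant medication form. This is an inference from the forms described; no section gives an example of it.

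At stake is the classification of some patients on the first key secondary endpoint, on which all later key secondary tests depend.

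**Working it through.** **Inputs.** Taper limit 7.5 mg/day, oral route only, Weeks 64 to 76 (SAP 4.3.1.2). Corticosteroid rescue from Week 64 at a mean of 20 mg/day or more over any 2 weeks (SAP 4.2.1.1). Scheduled dose 5 mg/day (Protocol 4.3.2.1). 126 patients per arm, CRR 30% on placebo and 50% on obinutuzumab, about 90% power (Protocol 6.1, SAP 2.2). The documents give no planning rate for the taper endpoint and no frequency of overlaps.

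**1. The plan's own figure.** With n = 126 per arm and mean proportion 0.40, the null standard error is √(2 × 0.40 × 0.60 / 126) = 0.0617, and the alternative is √((0.21 + 0.25) / 126) = 0.0604. Power = Φ((0.20 − 1.96 × 0.0617) / 0.0604) = 0.905, which agrees with the stated 90%.

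**2. Where the two scorings differ.** For concurrent records a and b, the SAP scores failure if max(a, b) > 7.5. The dose received breaches the limit if a + b > 7.5. They disagree only when both records are at most 7.5 and the sum exceeds 7.5, so the sum lies above 7.5 and at most at 15.

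| Records (mg/day) | Higher dose | SAP score | Sum | Score on dose received |
|---|---|---|---|---|
| 5 + 2.5 | 5 | success | 7.5 | success |
| 5 + 5 | 5 | success | 10 | failure |
| 7.5 + 2.5 | 7.5 | success | 10 | failure |
| 7.5 + 7.5 | 7.5 | success | 15 | failure |
| 5 + 10 | 10 | failure | 15 | failure |
| 10 + 2.5 | 10 | failure | 12.5 | failure |

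On top of the scheduled 5 mg/day, the affected range is an added dose above 2.5 and up to 7.5 mg/day. The rescue rule does not catch these patients, because 15 is below 20.

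**3. Size, under assumed frequencies.** Let s be the share of CRR patients affected. False successes per arm = 126 × CRR rate × s. This runs from 126 × 0.30 × 0.01 = 0.4 to 126 × 0.50 × 0.03 = 1.9. The scored difference exceeds the dose-received difference by 100 × (0.50 × s on obinutuzumab − 0.30 × s on placebo) points:

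- 1% in both arms: 0.5 − 0.3 = +0.2
- 3% in both arms: 1.5 − 0.9 = +0.6
- 3% obinutuzumab, 1% placebo: 1.5 − 0.3 = +1.2
- 1% obinutuzumab, 3% placebo: 0.5 − 0.9 = −0.4

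**4. Stress case beyond that range.** Take the taper rates as 30% and 50% (upper limits, since the endpoint requires CRR) and move patients to non-response:

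| Moved to non-response | Difference (points) | Power |
|---|---|---|
| 1 to 6 in each arm | 20.0 | 0.91 to 0.92 |
| 3, obinutuzumab only | 17.6 | 0.82 |
| 6, obinutuzumab only | 15.2 | 0.71 |
| 3, placebo only | 22.4 | 0.96 |
| 6, placebo only | 24.8 | 0.985 |

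Only an imbalance between arms matters much, and the documents give no reason to expect one in either direction.

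**The case against.** The strongest reply is about scope. The rules are introduced as a fallback for queries that cannot be resolved, overlaps are expected not to occur, and each record is meant to hold a total daily dose. Summing two such records would then double count. For a date overlap the rule is also conservative: a 10 mg/day record that runs past the start of a 5 mg/day record into Week 64 is scored a failure. This stands for date errors, and the higher-dose rule should stay for them.

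It does not cover confirmed co-administration. The same section also processes data that are not query failures, such as a final record marked ongoing. A query that confirms both drugs were taken leaves the overlap in the data with no other rule to score it. Nor does the SAP say that a single record must combine different agents.

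A second reply is that the protocol describes raising or substituting a dose rather than adding a second agent, and that its flare courses start at 20 mg/day or more (Protocol Appendix 5), which the higher-dose rule already fails. That is fair, and it suggests that the affected pattern is uncommon. It does not rule it out.

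A third reply concerns the remedy. Summing every overlap between different agents would wrongly fail a permitted switch: 5 mg/day prednisone to 5 mg/day prednisolone sharing one changeover day would count as 10 under a criterion that allows no receipt above 7.5. This is correct, and the fix below is limited for that reason.

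**Conclusion.** The point holds in a narrow form and is minor. For two oral steroids truly taken together, each at most 7.5 mg/day and totalling above 7.5 and up to 15, the SAP scores a CRR patient as a successful taper. That conflicts with the criterion and with the section's stated conservative intent. At an assumed 1% to 3% of CRR patients the effect is under two patients per arm and −0.4 to +1.2 points. Those shares are assumptions, the direction is unknown, and no bias in the gatekeeping test is shown.

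A reader might infer more than the documents support:

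- **That every patient above 7.5 mg/day in total passes.** Not so: one record above 7.5 fails the patient under the SAP rule, and CRR is also required.
- **That the primary endpoint is affected through the rescue criterion.** SAP 4.2.1.1 sets out the rescue conversion separately and does not invoke the overlap rule.
- **That cumulative corticosteroid dose is understated.** It is listed in SAP 1.1.1.3, but neither that section nor SAP 4.4 applies the rule to it.

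**What to change.** In SAP 4.3.1.2, before database lock:

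1. Keep the higher-dose rule for overlapping successive records (the same agent, or a changeover between substituted agents) and for overlaps judged to be date errors.
2. Sum prednisone-equivalent doses on days when records are confirmed as concurrent, whether a different agent or an add-on course.
3. Add a sensitivity analysis that sums all unresolved overlaps.

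A clause saying whether the overlap rule is confined to this endpoint would also remove doubt about rescue and cumulative dose.

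The cost is a few sentences, a small programming change and some query effort to label overlaps as concurrent or successive. In the sensitivity analysis a few date errors may be scored as failures. The sample size and the primary analysis do not change.

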3.1.4 Pharmacokinetic-Evaluable Population

The pharmacokinetic-evaluable population (PK population) will include all patients who have been randomized to and received any dose of obinutuzumab given as study medication, have at least one post-dose PK sample that is evaluable.

4. STATISTICAL ANALYSES

The primary analysis will be performed when all patients have completed the Week 76 visit or have withdrawn early from the study prior to Week 76, all data collected through

Week 76 are in the database, and the data have been cleaned and verified. At the time of the primary analysis, the study will be ongoing. General Consideration

Analyses of the primary and secondary efficacy endpoints will be stratified by race and region unless otherwise noted. The stratification factors as recorded in IxRS will be used.

All the endpoints will be analyzed and all outputs will presented by combined obinutuzumab and placebo treatment group unless otherwise specified. The treatment group in the document refers to combined obinutuzumab versus placebo group.

Visit windows will be continuous from the midpoint between two consecutive study visits, and will be dependent on the schedule of assessments for each variable independently. The exception will be Week 76 visit window. The upper limit of the Week 76 visit window will be 3 days prior to the next obinutuzumab or placebo infusion or 30 days beyond Week 76 whichever is shorter.

As 24-hour UPCR has been collected less frequently than the spot UPCR, the 24-hour UPCR will be windowed based on spot UPCR's schedule of assessments.

If there are multiple values in the same window, values closest to the scheduled study day will be used in the analysis. If two or more values are equidistant from the scheduled study day, the latest assessment will be used. For each patient, the day of first blinded infusion of obinutuzumab or placebo will be designated study Day 1. Each assessment will be assigned a study day calculated as:

date of assessment -date of first dose +1

Baseline definition: Baseline is defined as the last non-missing value prior to the receipt of blinded infusion of obinutuzumab or placebo. Typically, baseline will be the pre-dose Day 1 assessment, but may include screening results if the pre-dose Day 1 result is not available or missing.

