The proportions of patients achieving CRR in the obinutuzumab (combined treatment groups) and placebo groups will be compared using the CMH test with region and race as stratification factors. The proportion of patients achieving CRR in the obinutuzumab (combined) and placebo groups will be presented along with the adjusted difference, 95% confidence interval (CI) for the adjusted difference, and p-value. A summary of intercurrent events will be produced as well.

Missing data imputation will be performed by multiple imputations using data from patients who did not experience the intercurrent events that are handled using composite strategy, i.e., rescue therapy, treatment failure, death, and early study withdrawal. Prior to applying multiple imputations, missing 24-hour UPCR at any visit will first be imputed by Spot UPCR. Missing UPCR (when both 24-hour and spot UPCR are missing) and eGFR data for the primary endpoint CRR at Week 76 will be imputed by fully conditional specification (FCS) predicted mean matching method. This is also known as multivariate imputation by chained equations (MICE) and will follow the

method described in White et. al (2011). A set of candidate donors with 5 members is chosen for the predictive mean matching method. Separate imputation models will be used for each treatment arm. Only patients who did not experience the intercurrent events that are handled using the composite strategy, i.e., rescue therapy, treatment failure, death, and early study withdrawal, will be included in the imputation model.

UPCR and eGFR will be imputed using a single imputation model. The imputation model will specify UPCR at Week 76 as the dependent variable and will include eGFR at Week 76 as an auxiliary variable to be imputed as part of the MICE procedure. UPCR and eGFR at Week 24, 36, 50, 64 and 76 will be used in the analysis. As 24-hour UPCR is not collected at Weeks 36 and 64, spot UPCR will be used in the models for these time points.

The model will contain the following variables (in order of being imputed):

- Baseline UPCR
- Baseline eGFR
- Log-serum Albumin at Baseline
- Region (stratification factor)
- Race (stratification factor)
- Sex
- Age
- BMI
- Week 24 UPCR
- Week 24 eGFR
- Week 36 UPCR
- Week 36 eGFR
- Week 50 UPCR
- Week 50 eGFR
- Week 64 UPCR
- Week 64 eGFR
- Log-serum Albumin at Week 76
- Week 76 eGFR
- Week 76 UPCR

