The proportion of patients who achieve an ORR, defined as achievement of either CRR or PRR, evaluated at Week 50 will be analyzed using a CMH test with region and race as stratification factors. The definition of CRR is explained in Section 4.2.1. PRR is defined as achievement of all of the following:

- ≥50% reduction in UPCR from baseline
- UPCR <1 (or <3 if the baseline UPCR was ≥3)
- eGFR ≥85% of baseline, as calculated using the CKD-EPI equation
- No occurrence of the following intercurrent events:
 - Rescue therapy, treatment failure, death, or early study withdrawal

Intercurrent events are described in Section 4.2.1.1.

Missing data: Data obtained from the central laboratory only will be used.

Multiple imputations will be used for the missing data imputation using the model specified in Section 4.2.2. The analysis will follow the same methods described in Section 4.2.2.

4.3.1.4 Proportion of Patients who Experience Death or Renal-related Events through Week 76

Proportion of patients who experience death or renal-related events through Week 76, defined as the proportion of patients with one or more of the following events:

- Death
- Treatment failure (see Section 4.2.1.1)
- Worsening proteinuria, defined as a confirmed ≥ 50% increase in UPCR to a value ≥3
- Worsening eGFR, define as a confirmed ≥30% decrease in eGFR to a value <60

Worsening proteinuria and eGFR criteria will be evaluated by calculating the specified increase or decrease from the previous visit.

The death or renal related event will occur if any of the above events occur at any visit through Week 76. The proportion of patients who experience death or renal-related

events through Week 76 will be analyzed using a CMH test with region and race as stratification factors.

Estimand attributes for the endpoint are defined as follows:

- Population: patients with active or active/chronic ISN/RPS 2003 Class III or IV proliferative LN.
- Endpoint (variable): Death or renal-related events as defined above.
- Treatments:

Experimental: Obinutuzumab 1000 mg IV infusion at Day 1 and Weeks 2, 24, 26, and either Weeks 50 and 52 or Week 52 only

Control: Placebo

- Intercurrent events: Early study withdrawal prior to Week 76 due to lack of efficacy.
 It will be handled using composite strategy. That is, the early study withdrawals due to lack of efficacy will be considered as events.
- Summary measure: Difference in proportions at Week 76

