Early study withdrawals due to reasons other than lack of efficacy will be considered as having missing data.

The missing UPCR and eGFR values will be imputed by the multiple imputation model specified for the primary endpoint in Section 4.2.2 using data from the patients who did not experience death, treatment failure or early study withdrawal due to lack of efficacy.

The death or renal related event endpoint for patients who withdrew early from the study for reasons other than lack of efficacy will then be evaluated based on only the following criteria using the imputed UPCR and eGFR values:

- Worsening proteinuria, defined as a confirmed ≥50% increase in UPCR to a value ≥3
- Worsening eGFR, define as a confirmed ≥30% decrease in eGFR to a value <60

The death or treatment failure will not be imputed.

Worsening proteinuria will be assessed based on 24-hour UPCR which is collected at Week 24, 50 and 76 as per the protocol.

Imputation of eGFR will be made only for the Weeks 24, 36, 50, 64, and 76 as these visits are included in the imputation model (Section 4.2.2). If eGFR values worsened at other missing visits (Weeks 2, 4, 12, 26, and 52) that are not imputed, the worsening due to disease activity should be captured at the next observed or imputed visits. Study withdrawals who have not achieved the event following imputation of their UPCR or eGFR data will be assumed to have not had the event.

The multiple imputation parameters, analysis and pooling steps will be similar to the methods specified in the Section 4.2.2.

4.3.1.5 Mean Change in eGFR from Baseline to Week 76

Change in eGFR from baseline at Week 76 will be analyzed using Analysis of Covariance (ANCOVA) model. The response variable in the model will be change in eGFR from baseline at Week 76. Treatment group (combined obinutuzumab vs. placebo), baseline eGFR and the stratification factors race and region will be included in the model as independent variables. The adjusted difference between the treatment group with 95% CI and p-value will be presented.

The eGFR values for patients who died will be imputed with 0 (composite strategy). All other intercurrent events (specified in Section 4.3) will be handled using treatment policy strategy.

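### Does leaving the confirmation of a UPCR rise undefined cut late proteinuria events out of the death or renal-related events endpoint?

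*SAP*

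**What the plan says.** SAP Section 4.3.1.4 defines worsening proteinuria as a confirmed rise in UPCR of at least 50% to a value of at least 3. Protocol Sections 2.1.2 and 6.3.2.1 use the same terms. The SAP then fixes three things:

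- The reference value: "Worsening proteinuria and eGFR criteria will be evaluated by calculating the specified increase or decrease from the previous visit".
- The sample: "Worsening proteinuria will be assessed based on 24-hour UPCR which is collected at Week 24, 50 and 76 as per the protocol".
- The period: "The death or renal related event will occur if any of the above events occur at any visit through Week 76".

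The estimand line reads "Summary measure: Difference in proportions at Week 76".

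Spot UPCR appears elsewhere. In SAP Section 4.2.2, "missing 24-hour UPCR at any visit will first be imputed by Spot UPCR", and for the imputation model, "As 24-hour UPCR is not collected at Weeks 36 and 64, spot UPCR will be used in the models for these time points". The general rules in SAP Section 4 add: "As 24-hour UPCR has been collected less frequently than the spot UPCR, the 24-hour UPCR will be windowed based on spot" UPCR visits. They also say: "If there are multiple values in the same window, values closest to the scheduled study day will be used in the analysis".

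No section states which sample confirms a rise, within what interval, or against which earlier value. The same is true of the confirmed eGFR fall.

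**The concern.** Read narrowly, the 24-hour series has only three post-baseline points. If each rise must be confirmed by the next scheduled 24-hour sample, Week 24 is confirmed at Week 50 and Week 50 at Week 76, but nothing scheduled confirms Week 76. Under Protocol Appendix 1, Table 2, the Week 80 collection is taken only when the Week 76 one failed. A patient with UPCR of 3 or more at Week 76 also does not meet the listed criteria for continued blinded infusions in Protocol Section 3.1.2. Rises starting after Week 50 would then drop out of an endpoint that claims to run to Week 76.

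Two further points look open. The visit before Week 50 is Week 24 on the 24-hour series, but could be read as Week 36 if spot values count. A prompt repeat also falls in the same visit window as the sample it would confirm, and only one value per window is kept.

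The event count in a type-I-error-controlled endpoint is at stake. It is fourth in the key secondary sequence, with ORR and FACIT-F tested after it. Events missed at the same rate in both arms leave the risk ratio unchanged but shrink the reported difference in proportions.

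**Working it through.** **The plan's own figure.** The SAP states power only for the primary endpoint (SAP Section 2.2: 30% against 50%, 126 per arm, two-sided 0.05, about 90%). With pooled rate 0.40, power = Φ[(0.20 − 1.96·√(2·0.40·0.60/126)) / √((0.21 + 0.25)/126)] = Φ[(0.20 − 0.121)/0.0604] = Φ(1.31) = 90.5%. It reproduces, but says nothing about this endpoint, for which no event rate is given.

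**Schedule.** With next-24-hour confirmation, 2 of 3 assessments can yield an event. The uncovered stretch is 76 − 50 = 26 weeks, and 26/76 = 34%. That is a share of follow-up time, not of events.

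**Windows.** From study days 168, 252, 350, 448, 532 and 560, the midpoints are Day 210 and Day 399. The Week 76 window ends at Day 557 (560 − 3) or Day 562 (532 + 30), whichever is earlier. A repeat within 42 days after Week 24, 49 after Week 50 or 25 to 30 after Week 76 therefore shares the index visit's window.

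**What could confirm a rise.**

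- Protocol Appendix 5 gives near-identical renal flare criteria (a rise of at least 50% to above 3; a fall in eGFR of at least 30% from the previous assessment to below 60) and speaks of a repeated measurement.
- Protocol Section 4.6 asks for UPCR at unplanned visits for suspected flare. Appendix 1 sends those samples to the central laboratory.
- Protocol Appendix 3 takes both a 24-hour collection and a first-morning spot sample at every 24-hour visit, naming Week 76 as an example.

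So the narrow reading is one of several.

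**Illustrative size.** The documents give no onset times or durations, so these are assumptions: onset uniform over Weeks 12 to 76 and exponential duration with mean D. The chance of onset in (a, b] with UPCR still raised at Week w is P(a,b,w) = (D/64)·[exp(−(w−b)/D) − exp(−(w−a)/D)].

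Two rules are compared:

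- Strict 24-hour: P(12,24,50) + P(24,50,76).
- Spot-assisted (two consecutive central-laboratory samples, at least one of them 24-hour, both at least 3 and both at least 50% above the last value of the same type): P(12,24,36) + P(24,36,50) + P(36,50,64) + P(50,64,76).

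| D (weeks) | Strict 24-hour | Spot-assisted |
|---|---|---|
| 16 | 6.6% | 24.7% |
| 26 | 15.0% | 38.8% |
| 52 | 29.5% | 56.0% |
| permanent | 59.4% | 81.2% |

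Now assume true composite rates of 30% and 15%, 126 per arm and D = 26. If a share s of events shows only as proteinuria and a fraction d of those is counted, both rates are multiplied by f = 1 − s + s·d. The difference is 15·f points.

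| s | Rule | f | Difference (points) | Power |
|---|---|---|---|---|
| – | none missed | 1 | 15.0 | 81.8% |
| 10% | strict | 0.915 | 13.7 | 77.2% |
| 10% | spot-assisted | 0.939 | 14.1 | 78.5% |
| 30% | strict | 0.745 | 11.2 | 66.2% |
| 30% | spot-assisted | 0.816 | 12.2 | 71.1% |
| 50% | strict | 0.575 | 8.6 | 53.2% |
| 50% | spot-assisted | 0.694 | 10.4 | 62.5% |

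**Cost of using spot samples.** I simulated 2,000,000 patients with a stable true UPCR and assumed log-SDs of 0.25 (24-hour) and 0.35 (spot). False confirmed events at true UPCR 2.0 and 2.5 are 0.3% and 3.1–3.2% (strict) against 1.1% and 5.3% (spot-assisted). With s = 10% and every patient at 2.5, power is 70.9% strict and 68.5% spot-assisted, so the spot-assisted rule loses.

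**A trap in that rule.** Because Appendix 3 yields a 24-hour and a spot value at the same visit, the rule as worded lets a same-visit pair confirm. The share counted becomes P(12,24,24) + P(24,50,50) + P(50,76,76) = 53%, 66%, 81% and 100% for the four durations. A Week 76 rise would then count, and false events would be about 1.9% and 8.5%.

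**The case for a change.** The best case for a change is that the endpoint is formally tested and two programmers could build different event counts from the same data. The obvious answers are incomplete. Appendix 5 is an example written for steroid dosing, has a slightly different cut-off and is not cited by the endpoint. Flare visits list urinalysis UPCR, not a 24-hour collection. The imputed data for patients who withdrew have one value per scheduled visit, so no repeat exists for them. Treatment failure asks for sustained worsening, so it will seldom catch a rise first seen at Week 76, and SAP Section 4.6.6 says that criterion was not evaluated afterwards.

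It stands that the term is undefined, for eGFR as well as UPCR, and that no scheduled 24-hour sample within the Week 76 data can confirm a Week 76 rise. It also stands that a large share of proteinuria-only events would make the strict reading costly.

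The dispute over which series to use largely falls away. SAP Section 4.3.1.4 names the 24-hour series for this component, Protocol Section 6.3.1 uses 24-hour central-laboratory UPCR for efficacy, SAP Section 4.3.2.4 limits CRR onset to the same three weeks, and SAP Appendix 1 moved exploratory time points to match. The Week 36 and 64 spot values are there to feed the imputation model.

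**Conclusion.** No change to the plan is needed. The gap is real but is a matter of derivation detail. Analysts would have to settle it in the programming specification before lock, while still blinded, and the documents give them enough to do so sensibly. The headline loss of 26 weeks rests on a reading that no passage states and that conflicts with counting events at every visit to Week 76.

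Whichever rule is adopted applies equally to both arms. It creates no apparent bias between them and does not touch the primary result. Death, treatment failure, eGFR worsening (creatinine is also measured at Weeks 52, 64 and 76) and withdrawal for lack of efficacy still bring late worsening into the composite.

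The size is not known. The power figures depend wholly on assumed onset, duration, event rates, proteinuria-only share and assay error. They run from a gap of about 1 point (s = 10%) to about 9 points (s = 50%) between the two rules before false events are counted. Since treatment failure already counts sustained UPCR worsening from Week 24, a small share is plausible. The spot-assisted alternative gives up the plan's consistent 24-hour basis for noisier samples, brings its own ambiguity at Week 76, and is not clearly better.
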